B.2.7. Inclusion Criteria. Qualified subjects will meet all of the following criteria:

Patients of any gender, age 13-17 years
Inpatient psychiatric patients who have attempted suicide (lifetime) or have documented SI and a plan to harm themselves at admission
Understand written and spoken English
Own an iPhone with iOS 11 or higher, or Android with OS 8.1 or higher
Willing and able to complete enrollment procedures
Parent/guardian (and youth) able to understand the nature of the study and provide written informed consent (assent for youth)
Willing to agree to release of information to their parent/guardian and providers when clinically indicated.

B.2.8. Exclusion Criteria. Subjects who meet any of the following criteria are disqualified from this study:

Patients with active psychosis
Patients experiencing substance withdrawal

Currently enrolled in other treatment studies for the symptoms and behaviors targeted
Patient unwilling or unable to wear mask during in-person study procedures
Patients who, in the judgment of the investigator, would have an unfavorable risk/benefit profile with respect to [REDACTED]
Any other psychiatric or medical condition (e.g., intellectual disability) or custody arrangement that in the investigator's opinion would preclude informed consent/assent or participation in the trial.

B.2.9. Safety Evaluations. Adverse events (AEs) will be assessed at each study visit and will be reported according to Policy 910. AEs will be assessed with the questions "Have there been any changes to your physical health since the last study visit (or "start of the visit" if it is the first study visit)" and "Have there been any changes to your mental health since the last study visit (or "start of the visit" if it is the first study visit)". Assessments will be carried out throughout the study to help participants in need of more extensive support know when to contact their usual care provider and be guided to crisis contact services.

MILESTONE 3. Completion of the feasibility study within 6 months.

B.2.10. Data Processing and Analysis Plan. Data processing and analyses will be completed within 60 days and will be primarily descriptive. Data analyses will address the outcomes relating to the feasibility of [REDACTED] and study procedures. Data collected will be used to determine whether revisions should be considered before proceeding to a controlled trial.

MILESTONE 4. Completion of Data Processing and Data Analysis within 2 months.

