Enrollment Procedures. Eligible participants will be identified through medical record review. Consultations will be completed with participant's attending psychiatrists to confirm eligibility. Attending psychiatrists will be asked to inform the parent and patient that they will be contacted by staff about a research study; however, only IRB-approved study staff (without a treatment relationship with the patient) will recruit participants. When possible, parents and participants will be invited to participate in the study together. However, given that participants are inpatients and housed separately from parents, in most cases parents and patients will be invited to participate separately. When parents are not on site, IRB staff will call parents to invite them to participate. If parents agree, a remote consenting procedure will occur. Patients will all provide assent in person. Behavioral observations will be used as an additional indicator of assent. If patient's behavior does not indicate assent (e.g., avoiding eye contact, withdrawn) the participant will not be enrolled. Participants will not be recruited on the patient's first day of admission.

Retention Methods. We recognize that obtaining follow-up data is critical. Therefore, we will take several steps to optimize our ability to collect such data. During the informed consent process, participants (parents/guardians) will be asked to provide multiple forms of contact including a direct telephone contact and e-mail as well as the back-up numbers of at least two family members or friends in case study staff are unable to reach the participant at the direct number. If study staff is unable to reach the participant for follow-up at all contact numbers provided following no less than three call attempts, then a letter will be sent to the participant requesting that they contact the study staff. If no reply is received from 1 week of mailing the first letter, then a second letter will be sent requesting that the participant contact the study staff and also indicating a date by which study staff will no longer contact them to schedule follow-up calls. If no reply is received by the indicated date, then the participant will be considered lost to follow-up and will be withdrawn from the study.

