Early Withdrawal of Participants. Participants may voluntarily withdraw from the feasibility study at any time. They may contact the site PI at the phone number(s) listed on the informed consent document. Participants may be withdrawn from the feasibility study by the site PI if they no longer meet eligibility criteria, are unable to be contacted (lost to follow-up) or are otherwise unable to complete study procedures, or are determined to be adversely affected by content in [REDACTED]. Participants who attempt suicide while an active participant in the study will continue to be enrolled in the study so long as no criterion for withdrawal (e.g., no longer meet study criteria, adversely affect by content in [REDACTED]) is met. Participants will have access to the app for the duration of their participation in the study. Participants who withdraw or are withdrawn early from the feasibility study will no longer have access to the app.

PROTECTION OF HUMAN SUBJECTS

RISKS TO HUMAN SUBJECTS.

Human Subjects Involvement, Characteristics, and Design. The Institute of Living (IOL) leadership has consented to permit recruitment of patients to volunteer to participate in the feasibility study (see e-mail from [name], Medical Director). The proposed feasibility study will include 22 (of which 20 are expected to complete enrollment in the [REDACTED] app) adolescent patients from the IOL's CARES and Adolescent Psychiatry Units at Hartford HealthCare, who have attempted suicide (lifetime) or have clinically significant suicidal ideation and a plan to harm themselves.

Study Procedures, Materials, and Potential Risks. All participants will receive access to the Beta Version of [REDACTED] for the feasibility study. There are risks of emotional discomfort and distress from talking about suicide and other sensitive topics. There is also the risk that confidentiality may be broken.

ADEQUACY OF PROTECTIONS AGAINST RISKS.

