1.1 STUDY OBJECTIVES

1.1.1 PRIMARY OBJECTIVE

The primary objective of this study is to collect descriptive data to support feasibility, acceptability, safety, and potential for effectiveness.

- The potential for effectiveness is determined by examining participants' pre-test and post-test scores for SI and depression.
- The study will also collect data to guide refinements to the product and the workflow for product use.
- Participants will complete 12 sessions over approximately 12 weeks.
- Participants will complete assessments at baseline and weeks 1, 4, 8, and 12.
- Acceptability is determined from rates of session completion, rolling retention rate (percentage of participants who use the app on or after a set timeframe), and the system usability scale (SUS; Bangor et al., 2008), which indicates the extent to which participants found Oui's app usable.
- We will also conduct semi-structured user-feedback interviews.

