5 ADVERSE EVENTS

All adverse events (AEs) will be coded using the standardized Medical Dictionary for Regulatory Activities (MedDRA) central coding dictionary, version 24.1 or greater. AEs will be summarized in the safety population.

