5.2 SERIOUS ADVERSE EVENTS

Summaries of incidence rates and relationship to the investigational device of individual SAEs by SOC and PT will be prepared. Summaries will provide both the number of participants and the number of events within a reporting period. Percentages provided will be the percent of participants experiencing one or more serious adverse events.

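### A participant judged harmed by app content may be withdrawn from the whole study, and no app-only stop is described, so safety follow-up appears to end when that option is used

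*Protocol*

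**What the plan says.** **Withdrawal and access.** Under Early Withdrawal of Participants, the protocol gives the site investigator discretion to withdraw someone from the feasibility study on several grounds. One is a finding that app content has affected the participant adversely. App access lasts as long as study participation: "Participants who withdraw or are withdrawn early from the feasibility study will no longer have access to the app".

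**Suicide attempts.** The same section keeps a participant who attempts suicide enrolled "so long as no criterion for withdrawal (e.g., no longer meet study criteria, adversely affect by content in" the app (the product name is blacked out). Content harm is thus a named exception to staying in.

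**Loss of contact.** Under Retention Methods, after failed calls and two unanswered letters, "then the participant will be considered lost to follow-up and will be withdrawn from the study". Access to the app then ends too.

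**How safety data are collected.** Protocol B.2.9 states: "Adverse events (AEs) will be assessed at each study visit". The Timeline schedules AE, SIQ and C-SSRS assessment at weeks 1, 4, 8, 12 and 16 after the inpatient baseline. Under Risk Management, moderate or high risk at a study call leads to a contact with the parent or outpatient provider within 48 hours of that call.

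**How safety data are reported.** SAP 1.1.1 sets the primary objective as to "collect descriptive data to support feasibility, acceptability, safety, and potential for effectiveness". SAP 5 says "AEs will be summarized in the safety population" and does not define that population. SAP 5.2 reports both participants and events, and adds: "Percentages provided will be the percent of participants experiencing one or more serious adverse events". SAP 6.1.2 tabulates C-SSRS results at weeks 4, 8 and 12.

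**The concern.** Stopping an app that seems to be hurting an adolescent is plainly right. Ending observation at the same moment is a separate decision, and the plan joins the two. The ground for withdrawal is the harm that the study should detect, so any resulting loss of data would be related to the outcome.

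Two features add weight. First, the 48-hour risk contact depends on a study call taking place, so a participant with no further calls loses that protection as well as the measurement. Second, the protocol's AE Reporting section classes suicidal events as expected. That takes them out of the expedited route for unexpected, related and serious events, although study-related death has its own route. The visit data and final tables are therefore a main place where a content-related signal would appear. With 20 participants, one unseen case can change the impression that the tables give.

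**Working it through.** **1. The plan's own figure.** The only computable design figure is the number to consent (Protocol B.2.11): 20 × (1 + 0.10) = 22. Dividing instead gives 20 / 0.90 = 22.2, or 23. The point does not depend on this. The 10% covers losses before app enrolment only; neither document gives a withdrawal rate after enrolment.

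**2. Is an app-only stop described?** Early Withdrawal of Participants speaks of withdrawal from the study and ties access to participation. Retention Methods adds loss of contact as a route to withdrawal. No sentence in either document describes ending access while calls continue, or any assessment after withdrawal.

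**3. Follow-up lost, by time of withdrawal.** Calls are at weeks 1, 4, 8, 12 and 16 (Timeline); SAP C-SSRS points are at weeks 4, 8 and 12 (SAP 6.1.2). Weeks lost = 16 − week of withdrawal.

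| Withdrawn just after | Calls lost (of 5) | Weeks lost (of 16) | SAP C-SSRS points lost (of 3) |
|---|---|---|---|
| Week 1 | 4 | 15 | 3 |
| Week 4 | 3 | 12 | 2 |
| Week 8 | 2 | 8 | 1 |
| Week 12 | 1 | 4 | 0 |

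Protocol A.2 says that nearly half of suicide deaths in the year after psychiatric hospitalization fall in the first month after discharge. Taking that month as about four weeks, week 1 withdrawal loses about 4 − 1 = 3 of them. Withdrawal just after week 4, 8 or 12 loses essentially none.

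**4. SAE percentage.** Assume that the undefined safety population is the 20 enrolled. One participant is 1/20 = 5 points.
- No SAE before withdrawal and a first one afterwards: the reported percentage is 5 points too low.
- An SAE already counted, for example an attempt that met the seriousness criteria and led to withdrawal: 0 points. Later events would still be missing from the event count.
- No SAE at any time: 0 points.

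**5. C-SSRS table: direction.** Assume, for illustration, that 3 of 20 (15.0%) would show suicidal behaviour at week 8, and that 1 or 2 participants have been withdrawn for harm.
- If those withdrawn are among the 3: 2/19 = 10.5%, or 1/18 = 5.6%.
- If they are not: 3/19 = 15.8%, or 3/18 = 16.7%.

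The sign depends on who is withdrawn, which the documents do not tell us.

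**6. App use (secondary).** SAP 1.1.1 states: "Acceptability is determined from rates of session completion, rolling retention rate (percentage of participants who use the app on or after a set timeframe"). It gives no timeframe and no rule for access that the study ended. If x participants are seen using the app and k lost access before the timeframe, retention lies between x/20 and (x + k)/20. With assumed x = 12 and k = 2, that is 60% to 70%; excluding the two gives 12/18 = 66.7%.

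**The case against.** The strongest reply is that the rule is permissive. The investigator may withdraw a harmed participant but need not, and not using the app is not itself a listed ground for withdrawal. An investigator could advise an adolescent to stop the sessions and keep the calls. This stands. A reader might infer that every participant harmed by the app leaves safety follow-up, but the text makes that an option, not an outcome. What remains is that the option exists, that content harm is a named exception for suicide attempters, and that no alternative is written down.

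The end of follow-up is also inferred from silence. No sentence forbids later contact. The consent pages, Policy 910, the NIMH policy and the Risk Management Documentation Form were not available, and they might provide for it. This also stands, which is why follow-up only appears to end.

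On size, a reader might infer that each withdrawal for harm lowers the SAE percentage by 5 points, that the C-SSRS tables must look too favourable, or that early withdrawal always loses the peak-risk weeks. Steps 3 to 5 show that the first and third hold only under conditions, and that the second is plausible but not established.

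On app use, a reader might infer that access ended by the study cannot be told apart from disengagement. The documents do not support that. Attrition is a primary endpoint (Protocol B.2.2), disposition is summarized (SAP 3), and logins are tracked to week 16 (Timeline). The missing timeframe and denominator are reporting details.

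Finally, this is a small, single-group, descriptive study with no formal comparisons. That limits the statistical consequences, but it does not remove the reason to keep observing a suicidal minor thought to be harmed by the product.

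**Conclusion.** The concern holds in a limited form. The protocol permits study withdrawal because of the harm being studied and describes neither an app-only stop nor any assessment after withdrawal. When the option is used, AE and C-SSRS follow-up and the call-triggered risk contact appear to end.

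The loss is 4, 3, 2 or 1 of the 5 post-discharge calls for withdrawal just after week 1, 4, 8 or 12, and only the first case loses most of the first month. The SAE percentage is understated by 5 points per participant only when a first SAE follows withdrawal; this takes 20 as the denominator. The direction of any bias in the C-SSRS tables is plausible but not shown. The number withdrawn for harm is not given, and if it is zero nothing is lost.

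This is a cheap improvement worth making, not a flaw that invalidates the study. The app-use points do not carry it.

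**What to change.** **Protocol, Early Withdrawal of Participants.** When content is judged to have harmed a participant, or the app becomes unsuitable (for example, active psychosis), stop app access. With consent and assent, continue the already scheduled C-SSRS, SIQ and AE calls through week 16. Withdraw fully only when consent or assent is withdrawn or contact is lost.

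**SAP.** Record the date and reason that app access ended, and flag AEs and C-SSRS events that occur after it.

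**Optional clarification.** State the rolling-retention timeframe, and give retention and session completion with and without participants whose access the study ended.

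**Cost.** One protocol paragraph, minor consent wording and a few SAP lines. At most 4 calls continue per affected participant (3, 2 or 1 if the app stops after week 4, 8 or 12). Payments from week 4 on are at most 4 × $20 × 2 people + 2 × $25 bonus = $210 per adolescent and parent pair. That is within the 2 × $125 = $250 already provided in Protocol B.2.6. The real downside is further calls on a sensitive topic with a distressed adolescent, so they must stay voluntary.

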AE Reporting. Adverse events (AEs) will be monitored and documented at each study visit. Reporting of AEs will follow the Hartford HealthCare Institutional Review Board Policy 910 and NIMH policy. Given that all enrolled participants will have a history of suicidal ideation with plan, AEs related to suicidal thoughts/behaviors, including death by suicide, will be categorized as "expected". Further, AEs meeting any of the following criteria will be categorized as "Serious": results in death; is life-threatening (places the subject at immediate risk of death from the event as it occurred); requires inpatient hospitalization or prolongation of existing hospitalization; results in a persistent or significant disability/incapacity; results in a congenital anomaly/birth defect; an important medical event, based upon appropriate medical judgment, may jeopardize the subject's health and may require medical or surgical intervention to prevent one of the other outcomes listed in this definition; or results in a severely debilitating situation for the subject, such as psychological distress, financial hardship or damaging impact on social standing or employability. AEs which are unexpected, related, and serious will be reported to the HHC IRB within 7 calendar days and to the NIMH PO within 10 business days. Death related to the study will be reported to the NIMH PO within 5 business days. All other AEs will be documented and reported to HHC IRB and NIMH PO at the time of the respective annual progress reports.

OUI's DATA SECURITY AND RESOURCE SHARING PLAN

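### Labelling every suicidal AE as expected closes the prompt reporting route, so a serious, related, non-fatal suicidal event is scheduled only for the annual reports; reconcile with Policy 910 and NIMH policy

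*Protocol*

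**What the plan says.** Protocol, AE Reporting, sets four rules that bear on this point.

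- Classification: "AEs related to suicidal thoughts/behaviors, including death by suicide, will be categorized as" expected. No exception is made for severity, relatedness or worsening from baseline.
- Prompt route, IRB: "AEs which are unexpected, related, and serious will be reported to the HHC IRB within 7 calendar days". The same sentence then sets the limit for the NIMH program officer, for the same set of events: "and to the NIMH PO within 10 business days".
- Deaths: "Death related to the study will be reported to the NIMH PO within 5 business days". This sentence does not mention the IRB.
- Default: "All other AEs will be documented and reported to HHC IRB and NIMH PO at the time of the respective annual progress reports".

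The same section defers to outside rules: "Reporting of AEs will follow the Hartford HealthCare Institutional Review Board Policy 910 and NIMH policy". Protocol B.2.9 repeats part of this: "Adverse events (AEs) will be assessed at each study visit and will be reported according to Policy 910". The text of neither policy is in the documents.

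SAP 5.2 deals only with tabulation: "Summaries of incidence rates and relationship to the investigational device of individual SAEs by SOC and PT will be prepared". It sets no reporting timeline.

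**The concern.** The prompt route needs three conditions together, and the classification rule removes one of them in advance for the class of event that the app is meant to prevent. A serious, related, unexpected AE of any other kind would reach the IRB within 7 calendar days. A suicide attempt leading to hospitalization and judged related to the app would not.

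The protocol itself foresees such events. Early Withdrawal of Participants covers both suicide attempts during participation and harm from app content. The safeguards it describes work at the level of the individual: under Risk Management, increased risk is passed to the parent or guardian and the outpatient provider, with a follow-up contact within 48 hours for moderate or high risk; under Early Withdrawal, the site investigator may withdraw a participant, which ends app access. None of these steps informs the IRB that oversees the other minors using the same beta version. Safety is part of the primary objective in SAP 1.1.1. No estimate or analysis is affected; what is at stake is the timeliness of oversight.

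**Working it through.** The check is one of logic: apply the AE Reporting rules to every kind of suicidal AE.

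**Inputs, all from Protocol, AE Reporting**

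1. Suicidal AE: expected, by rule.
2. IRB, 7 calendar days: requires serious, related and unexpected.
3. NIMH program officer, 10 business days: same three conditions.
4. NIMH program officer, 5 business days: any death related to the study.
5. Everything else: annual progress report to each body.
6. Death is itself a seriousness criterion, so a fatal event is always serious. Life-threatening events and inpatient hospitalization also count as serious, so a non-fatal attempt can qualify.

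Serious, related and fatal give 2 × 2 × 2 = 8 combinations; the 2 that are fatal but not serious cannot occur, which leaves 6.

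| Suicidal AE | IRB | NIMH program officer |
|---|---|---|
| Not serious, unrelated | Annual | Annual |
| Not serious, related | Annual | Annual |
| Serious, unrelated, non-fatal | Annual | Annual |
| Serious, unrelated, fatal | Annual | Annual |
| Serious, related, non-fatal | Annual | Annual |
| Serious, related, fatal | Annual | 5 business days |

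For comparison, a non-suicidal AE that is serious, related and unexpected goes to the IRB in 7 calendar days and to NIMH in 10 business days. No suicidal AE reaches that route. The last two rows carry the point: the fifth has no prompt report to either body, and the sixth has none to the IRB. I found no other section that sends these events to the IRB sooner.

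**Size of the delay.** With an annual cycle and no dates, the wait from event to next report lies between 0 and 12 months. Milestone 3 has the study completed within 6 months. Suppose it takes the full 6 months and the annual clock starts L months before the study does. The first annual report then falls at study month 12 − L. That is after the study ends if 12 − L > 6, that is L < 6, and during the study if L > 6. The documents do not give L for either body, so the supported statement is a delay of up to one annual reporting cycle.

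**Stated reason for the label.** AE Reporting justifies it by saying that every participant will have had ideation together with a plan. B.2.7 admits patients on either a lifetime attempt or documented ideation with a plan, so the reason does not describe everyone eligible. This changes no row of the table.

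**The case against.** The strongest reply is that Policy 910 and NIMH policy govern. The protocol commits to following both. If either requires faster reporting of these events, the commitment is already made and the fault is an inconsistency within the text. If neither does, the plan complies with the rules of the two bodies concerned, and asking for more is a view on oversight. That stands in part: a reader might infer that the protocol breaches Policy 910 or NIMH policy, and the documents do not support this, because neither text is available. It does not remove the point. In the first case staff have a specific sentence that contradicts the general commitment; in the second, the protocol's own rule still delays oversight of events it foresees.

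It is also fair to say that the classification is openly stated and reasoned, that suicidal events are to be anticipated in this population, and that individual safeguards are in place. A reader might infer that participants are left unprotected after an event; Risk Management and Early Withdrawal show otherwise. The objection here is only to a descriptive label also deciding whether a related, serious event is reported promptly.

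A reader might further infer that the IRB would learn of an event only after the last participant has finished. That depends on report dates that are not given, as shown in the working. Likewise, it would be wrong to say that no suicide death is reported promptly: a study-related one goes to NIMH within 5 business days.

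**Conclusion.** The point holds on the protocol's text as written. A serious, related, non-fatal suicidal event is scheduled for the annual reports to both bodies, and a study-related suicide death has no stated prompt report to the IRB. The delay is up to one annual reporting cycle, against 7 calendar days (IRB) and 10 business days (NIMH) for other serious, related, unexpected AEs. No number of affected events can be given, because the documents contain no rate of serious, related suicidal events.

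The conclusion assumes that the specific sentences of AE Reporting are applied literally. Whether they conflict with the two policies cannot be settled from these documents, and confidence is moderate for that reason. It should be fixed because the trial enrols minors at high risk of suicide and the change is small. The mismatch between the stated reason and B.2.7 is a minor wording matter.

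**What to change.** 1. Compare AE Reporting with Policy 910 and NIMH policy and reconcile any difference.
2. Keep expected as a descriptive label. Subject to those policies, reword the prompt-reporting sentence so that the existing windows (7 calendar days to the IRB, 10 business days to the NIMH program officer) cover AEs that are serious, related, and either unexpected or suicidal in nature. For the IRB this should include a related suicide death.
3. Leave the sentence on study-related deaths as it is. It covers any such death, suicidal or not, and folding its 5-business-day limit into the new sentence would narrow it.
4. Reword the reason for the label to match B.2.7: a lifetime attempt, or documented ideation with a plan.

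The cost is one or two sentences of protocol text and a few extra expedited reports among 20 to 22 participants, never more than the number of serious, related suicidal events. Relatedness would have to be judged promptly for each serious suicidal event. SAP 5.2 already needs a relationship judgement for every SAE, so mainly its timing is new.
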